2.0 Goals**2.1 Primary Goal**

To estimate the proportion of women who have adequate estrone (E1) and estradiol (E2) suppression after 8-10 weeks of adjuvant anastrozole 10 mg once daily (ANA10) having had inadequate E1 and E2 suppression after 8-10 weeks of standard dose anastrozole 1 mg once daily (ANA1).

2.2 Secondary Goals

- 2.21 To estimate the proportion of women with elevated E1 and E2 levels after 8-10 weeks of adjuvant ANA1.
- 2.22 To estimate the proportion of women with elevated E1 and E2 levels after 8-10 weeks of adjuvant ANA1 whose E1 and E2 levels remain elevated after 8-10 weeks of adjuvant ANA10.
- 2.23 To examine the toxicity profile of ANA1 over the 8-10 weeks of treatment, ANA10 over the 8-10 weeks of treatment, and letrozole over the 8-10 weeks of treatment.
- 2.24 To examine concentrations of anastrozole at both the ANA1 and ANA10 dose levels.
- 2.25 To examine E1 and E2 concentrations, as well as letrozole drug levels, in patients receiving letrozole (following ANA10).
- 2.26 To bank DNA for examination of SNP-set(s) determined in the ongoing Mayo Clinic Breast Cancer SPORE Project 4

2.3 Exploratory Objectives

To examine the association between clinical variables such as age, age at menopause, BMI, receipt of chemotherapy, chemotherapy regimen, and dose on E1 and E2 levels after 8-10 weeks of ANA10.

3.0 Registration Patient Eligibility**3.1 Registration - Inclusion Criteria**

3.11 Women of age ≥ 18 years.

3.12 Disease characteristics:

- 3.121 Histological confirmation of invasive breast carcinoma.
- 3.122 Stage I-III breast cancer
- 3.123 Estrogen receptor (ER) positive disease according to ASCO/CAP guidelines as ER $\geq 1\%$ positive nuclear staining.

3.13 Completion of all planned cancer treatments prior to registration:
1) surgical resection of breast and nodal surgery;
(NOTE: Reconstructive surgery does not have to be completed)
2) adjuvant radiation therapy, if needed;
3) and neoadjuvant and/or adjuvant chemotherapy, if needed.

3.14 Post-menopausal defined as

- Age ≥ 60 and amenorrhea >12 consecutive months
OR
- Previous bilateral oophorectomy
OR
- Age <60 and amenorrhea >12 consecutive months and documented follicle stimulating hormone (FSH) level within post-menopausal range according to institutional standard

NOTE: Patients who did not meet these criteria at time of diagnosis and received pre-operative (neoadjuvant) or post-operative (adjuvant) chemotherapy will not be allowed to participate.

3.15 ECOG Performance Status (PS) 0, 1, or 2 ([Appendix I](#)).

3.16 The following laboratory values obtained ≤ 14 days prior to registration:

- Hemoglobin ≥ 8.0 g/dL
- Absolute neutrophil count (ANC) $\geq 1500/\text{mm}^3$
- Platelet count $\geq 70,000/\text{mm}^3$
- Total bilirubin $\leq 1.5 \times \text{ULN}$
- Alanine aminotransferase (ALT) and aspartate transaminase (AST) $\leq 3 \times \text{ULN}$

3.17 Ability to swallow oral medication

3.18 Provide written informed consent.

3.19a Willingness to provide mandatory blood specimens for correlative research (see Section 14.0).

3.19b Willing to return to enrolling institution for follow-up (during the Active Monitoring Phase of the study).

3.2 Registration - Exclusion Criteria

3.21 Pre-menopausal women receiving ovarian function suppression (goserelin, leuprolide, etc.)

3.22 Stage IV (metastatic) breast cancer.

3.23 HER2 positive breast cancer as defined by

- HER2 IHC $\geq 3+$
- HER2/CEP17 ≥ 2.0
- HER2/CEP17 < 2.0 and average HER2 copy number of ≥ 6.0 signals/cell

3.24 Prior endocrine therapy for this breast cancer.
Exceptions:

- 1) Pre-operative aromatase therapy (anastrozole, letrozole, or exemestane) and last treatment was ≥ 4 weeks prior to registration
OR
- 2) Pre-operative tamoxifen therapy and last treatment was ≥ 12 weeks prior to registration

3.25 Currently receiving any of the following cancer-directed therapies:

- Radiation therapy
- Systemic therapy such as chemotherapy (standard or investigational)

3.26 Bisphosphonate therapy started < 4 weeks prior to registration.
NOTE: If patient is currently on bisphosphonate therapy she must be on stable dose for ≥ 4 weeks prior to registration.
Patients not currently taking bisphosphonates will be allowed to start bisphosphonate therapy after completion of anastrozole (1mg and 10 mg daily (if given)). Information regarding bisphosphonate therapy will be collected.

3.27 Current use of systemic or topical exogenous estrogen or progesterone (menopausal hormone replacement therapy [HRT]).

3.28 Prior ovarian function suppression (leuprolide, goserelin, etc.).

3.29a Inability to provide informed consent.

3.29b History of contralateral DCIS or invasive breast cancer.
NOTE: Exception allowed if

1. Patient did not receive adjuvant endocrine therapy
OR
2. Patient received adjuvant endocrine therapy but has been off treatment for at least 6 months prior to registration

3.29c Concurrent active malignancy or history of malignancy ≤ 3 years prior to registration.
NOTE: Exceptions allowed for successfully treated cervical carcinoma in situ, lobular carcinoma in situ of the breast, papillary thyroid cancer, or non-melanoma skin cancer.

3.29d Prior prevention therapy with an aromatase inhibitor or a SERM.
Exception: Therapy with a SERM (tamoxifen or raloxifene) is allowed if patient has been off treatment for ≥ 6 months prior to registration.

3.3 Re-Registration – Inclusion Criteria

3.31 Confirmation that baseline blood sample was drawn and submitted.

3.32 Blood estrogen levels after Cycle 1anastrozole (ANA1) must meet the following criteria:
 $E1 \geq 1.3 \text{ pg/ml}$, AND
 $E2 \geq 0.5 \text{ pg/ml}$

4.0 Test Schedule

4.1 Test schedule for breast cancer

Tests and procedures	Active Monitoring Phase								
	≤14 days prior to registration	At end of Cycle 1 ¹	Re-registration	After ReReg and prior to Tx on C2D1 ²	Nurse call 2-4 weeks after starting ANA10	First 6 pts: once during Cycle 2 Days 28-35 ³	At end of Cycle 2 ⁴	30 days after last dose of ANA10	At end of Cycle 3
Window	±7 days			±7 days		±7 days	±3 days	+14 days	
History and exam ⁵	X	X		X ⁶					X
Height and weight ⁷	X	X					X ^R		X
Adverse event assessment, vital signs (BP, pulse), ECOG PS	X	X		X	X ⁸	X ^R	X ^R	X ^R	X
Hematology: CBC/differential	X	X ^R				X ^R	X ^R	X ^R	
Chemistries: alanine transaminase (ALT), aspartate transaminase (AST), total bilirubin	X	X ^R				X ^R	X ^R	X ^R	
Research blood specimens (see Section 14.0) ^R	X ^R	X ^{R9}					X ^R		X ^R
Medication Diary		X					X		X

Cycle = 56-70 days (8-10 weeks), R= Research funded

¹ Approximately 9 weeks after start of ANA1 ±7 days; or at discontinuation of ANA1 if that event occurs earlier than 8-10 weeks.

² Visit to obtain prescription after blood results are received.

³ One-time safety assessment for first six patients who re-register to ANA10

⁴ Approximately 9 weeks after start of ANA10 ±7 days; or at discontinuation of ANA10 if that event occurs earlier than 8-10 weeks. Must be prior to starting letrozole.

⁵ Physical exam is required at baseline. After baseline, physical exam may be performed at any time as clinically indicated, but is not required for protocol.

⁶ Nurse visit for ANA10 education (prior to starting ANA10)

⁷ Only weight needed after baseline

⁸ Call to assess/collect adverse events and verify patient is taking ANA10 and wants to continue (no vital signs or PS); Refill ANA10 by mail if needed

⁹ E1 and E2 results required prior to re-registration.

4.2 Survival Follow-up

This study does not follow patient survival. Once patients complete protocol treatment and procedures they are off study.

5.0 Stratification Factors: None

6.0 Registration/Randomization Procedures

6.1 Registration (Step 1)

To register a patient, access the Mayo Clinic Cancer Center (MCCC) web page and enter the registration/randomization application. The registration/ randomization application is available 24 hours a day, 7 days a week. Back up and/or system support contact information is available on the website. If unable to access the website, call the MCCC Registration Office at [REDACTED] between the hours of 8 a.m. and 4:30 p.m. Central Time (Monday through Friday).

The instructions for the registration/randomization application are available on the MCCC web page [REDACTED] and detail the process for completing and confirming patient registration. Prior to initiation of protocol treatment, this process must be completed in its entirety and an MCCC subject ID number must be available as noted in the instructions. It is the responsibility of the individual registering the patient to confirm the process has been successfully completed prior to release of the study agent. Patient registration via the registration/randomization application can be confirmed in any of the following ways:

- Contact the MCCC Registration Office [REDACTED] If the patient was fully registered, the MCCC Registration Office staff can access the information from the centralized database and confirm the registration.
- Refer to “Instructions for Remote Registration” in section “Finding/Displaying Information about A Registered Subject.”

6.2 Verification of materials

Prior to accepting the registration, registration/randomization application will verify the following:

- IRB approval at the registering institution
- Patient eligibility
- Existence of a signed consent form
- Existence of a signed authorization for use and disclosure of protected health information

6.3 Documentation of IRB approval

Documentation of IRB approval must be on file in the Registration Office before an investigator may register any patients.

In addition to submitting initial IRB approval documents, ongoing IRB approval documentation must be on file (no less than annually) at the Registration Office [REDACTED] [REDACTED] If the necessary documentation is not submitted in advance of attempting patient registration, the registration will not be accepted and the patient may not be enrolled in the protocol until the situation is resolved.

When the study has been permanently closed to patient enrollment, submission of annual IRB approvals to the Registration Office is no longer necessary.

6.4 Correlative Research**6.41 Mandatory**

A mandatory correlative research component is part of this study, the patient will be automatically registered onto this component (see Sections 3.19a and 14.0).

6.42 Banking

At the time of registration, the following will be recorded:

- Patient has/had not given permission to store and use her/his data and sample(s) for future research on cancer at Mayo.
- Patient has/had not given permission to store and use her/his data and sample(s) for future research to learn, prevent, or treat other health problems.
- Patient has/had not given permission for MCCC to give her/his data and sample(s) to researchers at other institutions.

6.5 Treatment on protocol

Treatment on this protocol must commence at Mayo Clinic under the supervision of a medical oncologist.

6.6 Treatment start

Treatment cannot begin prior to registration and must begin ≤ 21 days after registration.

6.7 Pretreatment

Pretreatment tests/procedures (see [Section 4.0](#)) must be completed within the guidelines specified on the test schedule.

6.8 Baseline symptoms

All required baseline symptoms (see [Section 10.6](#)) must be documented and graded.

6.9a Study drug

Study drug is available on site.

6.9b Blood draw kits

Blood draw kit is available on site for sites outside of Rochester, Minnesota.

6.9c Study Conduct

The clinical trial will be conducted in compliance with regulations (21 CFR 312, 50, and 56), guidelines for Good Clinical Practice (ICH Guidance E6), and in accordance with general ethical principles outlined in the Declaration of Helsinki; informed consent will be obtained from all participating patients; the protocol and any amendments will be subject to approval by the designated IRB prior to implementation, in accordance with 21 CFR 56.103(a); and subject records will be stored in a secure location and subject confidentiality will be maintained. The investigator will be thoroughly familiar with the appropriate use of the study drug as described in the protocol and Investigator's Brochure. Essential clinical documents will be maintained to demonstrate the validity of the study and the integrity of the data collected. Master files should be established at the beginning of the study, maintained for the duration of the study and retained according to the appropriate regulations.

6.9d Re-registration (Step 2)

6.9d1 To re-register a patient, access the Mayo Clinic Cancer Center (MCCC) web page and enter the registration/randomization application. The registration/randomization application is available 24 hours a day, 7 days a week. Back up and/or system support contact information is available on the website. If unable to access the website, call the MCCC Registration Office at [REDACTED] between the hours of 8 a.m. and 4:30 p.m. Central Time (Monday through Friday).

NOTE: Re-registration to Cycle 2 will be temporarily halted once 6 patients have been re-registered for a safety run-in.

6.9d2 Treatment cannot begin prior to re-registering to the second phase and will begin ≤ 14 days after registration to the second phase.

7.0 Protocol Treatment

7.1 Treatment Schedule

7.11 Treatment medication table

Cycle	Agent	Dose Level	Route	Day	Duration
1	Anastrozole	1 mg	oral	daily	8-10 weeks
2	Anastrozole	10 mg	oral	daily	8-10 weeks
3	Letrozole	2.5 mg	oral	daily	8-10 weeks

7.2 Agents

Anastrozole and letrozole are oral agents commonly used as adjuvant treatment for ER-positive breast cancer to reduce the risk of recurrence.

Protocol treatment should be taken at the same time every day (morning preferred) and may be taken without regard for food. EXCEPTION: On the day of the end of cycle blood draw, the treatment should be taken after the blood draw is completed.

7.3 Cycle 1 Anastrozole (ANA1)

7.31 Basics

A research blood sample must be drawn at baseline prior to treatment or patient is unevaluable and must be replaced.

All patients will be prescribed the FDA-approved dose of anastrozole at 1mg daily (standard adjuvant dose) for the first 8-10 weeks.

At the end of the first cycle, blood will be drawn for drug levels and E1 and E2 levels.

Patients should be encouraged to take their anastrozole in the morning each day EXCEPT the day of the blood draw when they should take their anastrozole after this sample has been drawn.

7.32 Blood draw at end of cycle

Patients will have blood drawn for estrone and estradiol concentrations and all samples for the week will be batched for processing in the Immunochemical Core Laboratory the following Monday.

Results will be reported the following day (usually Tuesday).

Patients who do not meet the following criteria will be given a recommendation for 5 years of anastrozole and go off study.

E1 \geq 1.3 pg/ml

AND

E2 \geq 0.5 pg/ml

Patients whose estrogen levels meet these criteria and are willing to continue will proceed to Cycle 2.

NOTE: Patients unwilling to continue will go off study and be replaced.

7.33 Logistics

Study team will contact patients by telephone and tell the patients to either:

1) Continue anastrozole 1mg and go off study.

OR

2) Come to the clinic for an appointment in the next couple weeks (prior to running out of ANA1) to re-register and obtain the new prescription.

Re-registration is required for these patients prior to Cycle 2.

7.4 Cycle 2 Anastrozole (ANA10)

7.41 Safety run-in period (first six patients re-registered to ANA10)

Re-registration will temporarily halt after maximum of 6 patients have been re-registered to the study.

Re-registered patients will be given a 4-5 week supply of anastrozole 10 mg (ANA10) daily.

A study nurse will call patients after 2-3 weeks to review AEs and determine whether patients are willing to continue ANA10.

Also, after 28-35 days of ANA10 treatment, first six patients will return to registering institution for adverse event monitoring. A patient is considered to have developed a DLT if any of the following serious adverse event definitely, probably, or possibly attributed to anastrozole 10 mg occurs within 28-35 days of starting ANA10.

CTCAE SOC	DLT Definition
Cytopenias (including Blood and lymphatic system disorders and Investigations)	Grade 4 Neutrophil count decreased lasting >7 days \geq Grade 3 Platelet count decreased with clinically significant bleeding Febrile neutropenia
Hepatobiliary disorders	\geq Grade 3 Hepatic failure: Any drug-induced liver injury (DILI) (AKA Hy's Law cases)

CTCAE SOC	DLT Definition
Unspecified	
Any ≥Grade 3 adverse event per NCI Common Terminology Criteria for Adverse Events v5.0, excluding the following:
 
 Any ≥Grade 3 electrolyte alteration* lasting ≤72 hours, is not clinically complicated, and resolves spontaneously or responds to conventional medical interventions Any ≥Grade 3 serum amylase increased or lipase increased not associated with symptoms or clinical manifestations of pancreatitis Grade 3 nausea, vomiting, or diarrhea (lasting ≤72 hours) which responds to maximal supportive treatment(s) Grade 3 fatigue (even if it lasts >1 week)
Death	Any death occurring in these patients during treatment or during 30 days after last dose

*Electrolyte alterations may include the following events in SOC “Metabolism and nutrition disorders”

- Hypercalcemia or Hypocalcemia
- Hyperglycemia or Hypoglycemia
- Hyperkalemia or Hypokalemia
- Hypermagnesemia or Hypomagnesemia
- Hypernatremia or Hyponatremia
- Hyperphosphatemia or Hypophosphatemia

If 1 of the first 6 patients enrolled in the safety run-in experience any dose limiting toxicities (DLTs) (as defined in Section 7.4.1 above), attributed (definitely, probably, or possibly) to anastrozole 10mg the FDA must be notified immediately.

If two or more of these 6 patients develops a DLT (as specified in Section 7.0 of the protocol) within 28-35 days of starting ANA10, the study will remain closed to enrollment to allow the study team to review toxicity data thoroughly and make decisions regarding changes to the protocol. If at most one of these 6 patients develops a within 28-35 days of starting ANA10, re-registered will reopen.

Patients who develop a DLT will have a research blood draw and go to the extended follow-up phase where an adverse event assessment will be undertaken 28-35 days after treatment discontinuation.

Patients who do not develop a DLT and are willing to continue, will have the remaining ANA10 supply (5-6 weeks) shipped to the patient by FedEx.

At the end of the second cycle, or at discontinuation of ANA10, blood will be drawn for drug levels and E1 and E2 levels.

Patients should be encouraged to take their anastrozole in the morning each day EXCEPT the day of the blood draw when they should take their anastrozole after this sample has been drawn.

Patients who complete Cycle 2 will proceed to Cycle 3.

Patients unable to complete Cycle 2 will have research blood draw and then go to extended follow-up where an adverse event assessment will be undertaken 28-35 days after treatment discontinuation.

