16.4 Stopping rules

16.41 Feasibility stopping rule

The percentage of patients who have inadequate estrogen suppression ($E1 > 1.3 \text{ pg/ml}$ and $E2 > 0.5 \text{ pg/ml}$) will be examined after every 25th patients has completed 8-10 weeks of anastrozole at the 1 mg daily dose. If this percentage is 10% or less among these 25 patients and all the previously enrolled patients is 10% or less, the trial will temporarily halt for the study team to review study data to make a trial recommendation to FDA and IRB.

16.42 Safety Stopping rule:

Adverse events will be examined at the completion of each treatment. Enrollment to the trial will be temporarily halted if:

- (a) During or at completion of treatment Cycle 1 with anastrozole 1 mg daily, 2 or more of the first 6 patients or 30% or more of the patients treated with the agent have developed a Grade 4 cytopenia or some other Grade 3-4 adverse event during or at completion of that agent
- (b) During or at completion of treatment Cycle 2 with anastrozole 10 mg daily, if 2 or more of the first 6 patients develops a DLT (as specified in Section 7.0 of the protocol) within 28-35 days of starting ANA10. The study will remain closed to enrollment to allow the study team to review toxicity data thoroughly and make decisions regarding changes to the protocol. If at most one of these 6 patients develops a DLT within 28-35 days of starting ANA10, re-registration will reopen.

After at least 7 patients have been re-registered and have begun ANA10, 30% or more of the patients treated with the agent have developed a Grade 4 cytopenia or some other Grade 3-4 adverse event during or at completion of that agent

- (c) During or at completion of treatment Cycle 3 with letrozole 2.5 mg daily, 2 or more of the first 6 patients or 30% or more of the patients treated with the agent have developed a Grade 4 cytopenia or some other Grade 3-4 adverse event during or at completion of that agent
- (d) A patient death on protocol treatment or within 30 days of discontinuing all protocol treatment that is considered possibly, probably or definitely related to treatment.

The study team will review study data and then make a trial recommendation to FDA and IRB.

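### The 10 mg run-in gate and the 30% halt rule count different events, so re-registration can reopen on data that meet the halt rule once a seventh woman starts

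*Combined protocol and SAP*

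**What the plan says.** **The run-in gate (Sections 1.41, 7.41 and 16.42(b)).** Re-registration to 10 mg pauses after six women. Two or more with a DLT keep the study closed for review. Otherwise: "If at most one of these 6 patients develops a DLT within 28-35 days of starting ANA10, re-registration will reopen". A DLT must be at least possibly attributed to 10 mg and occur within 28-35 days of starting it.

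The cytopenia row of the DLT table lists "Grade 4 Neutrophil count decreased lasting >7 days", febrile neutropenia, and, at that grade or higher, "Grade 3 Platelet count decreased with clinically significant bleeding". A later row, labelled as unspecified, takes in any event of Grade 3 or higher apart from four exclusions: electrolyte changes of up to 72 hours, amylase or lipase rises without pancreatitis, Grade 3 nausea, vomiting or diarrhea of up to 72 hours, and "Grade 3 fatigue (even if it lasts >1 week").

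**The broad rule (Section 16.42).** The event counted is "a Grade 4 cytopenia or some other Grade 3-4 adverse event". There is no condition on duration, bleeding or attribution, and fatigue is not excluded.
- For 1 mg and for letrozole, parts (a) and (c) halt enrollment at "2 or more of the first 6 patients or 30% or more of the patients treated with the agent".
- For 10 mg, part (b) applies the DLT rule to the first six and brings in the broad count later: "After at least 7 patients have been re-registered and have begun ANA10, 30% or more of the patients treated with the agent". Its denominator is everyone treated at 10 mg, so the first six are in it.

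Every halt under Section 16.42 is temporary and leads to a review by the study team.

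**The concern.** The run-in was requested by the FDA as the check before more women take ten times the approved dose. Under the present wording, events that Section 16.42 treats as grounds for a halt can already be on file when the sixth woman is assessed, yet they play no part in the decision to reopen. They are used only after another woman has started 10 mg.

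At the two approved doses the same broad count applies within the first six. The documents give no reason for starting it one patient later at the experimental dose. What is at stake is the timing of a safety review, not the efficacy result.

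**Working it through.** **The plan's own figure.** The plan states no operating characteristics for its safety rules. Its one computed design figure is the efficacy power in Section 16.1. With 29 women, rejection at 12 or more, and rates of 25% and 50%, the exact one-sided level is 0.0390 and the power 0.8675, which agrees with the stated 87%. Nothing below changes it.

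**Step 1: the 30% limit as a count.** The limit is the smallest k with k/n at or above 0.30.
- n = 6: k = 2 (2/6 = 33.3%)
- n = 7 to 10: k = 3 (3/7 = 42.9%, 3/10 = 30.0%; 2/7 = 28.6% falls short)
- n = 11 or 12: k = 4

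**Step 2: the rules applied to six women.** Here a *gap event* is one that Section 16.42 counts but that is not a DLT. Grade 3 fatigue is the clearest case.

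| First six at 10 mg | Run-in gate | Same count at 1 mg or letrozole | When a seventh woman starts 10 mg |
|---|---|---|---|
| 2 gap events, 0 DLTs | reopens | halt (33.3%) | no halt unless she has an event (28.6%) |
| 3 gap events, 0 DLTs | reopens | halt (50.0%) | halt limit met (42.9%) |
| 2 gap events, 1 DLT that 16.42 also counts | reopens | halt (50.0%) | halt limit met (42.9%) |

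This step needs no assumed rate. Three events stay at or above 30% up to ten women, so a short delay in looking does not remove the conflict.

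**Step 3: how often.** The documents give no event rate at 10 mg. Let g be an assumed per-woman rate of gap events, with women independent and no DLTs. X is the number among six, binomial(6, g).
- P(X ≥ 2) = 1 − (1−g)^6 − 6g(1−g)^5. At g = 5%: 1 − 0.7351 − 0.2321 = 0.0328.
- P(X ≥ 3) = P(X ≥ 2) − 15g²(1−g)^4. At g = 5%: 0.0328 − 0.0305 = 0.0022 (from unrounded terms).
- P(X = 2 and none in the seventh) = 15g²(1−g)^5. At g = 5%: 0.0290.

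| g (assumed) | 2 or more of six: would halt 1 mg or letrozole | 3 or more of six: reopens, limit met at seven | Exactly two of six, none in the seventh: no halt at six or seven |
|---|---|---|---|
| 1% | 0.15% | 0.002% | 0.14% |
| 5% | 3.3% | 0.2% | 2.9% |
| 10% | 11.4% | 1.6% | 8.9% |
| 20% | 34.5% | 9.9% | 19.7% |
| 30% | 58.0% | 25.6% | 22.7% |

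**Step 4: allowing for DLTs.** Add an assumed 5% DLT rate, with every DLT also counted by Section 16.42. The chance that the gate passes with three or more counted events becomes 0.8% at g = 5% and 3.4% at g = 10%. With two or more it becomes 8.1% and 19.1%.

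**The case against.** The best defense is that these are two rules with two purposes. The gate asks about toxicity attributed to 10 mg, and the fatigue exclusion, worded to apply even when fatigue persists, looks deliberate. Section 16.42 is a wider net with no attribution filter, taking over once the run-in is done. Cycle 2 is also the only cycle with a hard pause at six, an early nurse call, a dedicated safety visit and immediate FDA notification of a single DLT. Section 8.2 stops anastrozole in any woman with a related Grade 3 or 4 event, and Section 16.61 provides monthly review. All of this stands, and it limits the harm. None of it holds re-registration of further women when the broad count is already at its limit.

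A second argument is that a two-of-six hold would occur far more often than the conflict it removes: 3.3% against 0.2% at g = 5% (about 15 times), and 11.4% against 1.6% at g = 10% (about 7 times). That is correct. The answer is that two of six is the limit the plan already sets for the approved doses, and that a three-of-six version of the fix avoids this cost.

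Three stronger readings are tempting, and the documents do not support them:
- **That the gate ignores Grade 4 cytopenias.** Several are DLTs: prolonged Grade 4 neutropenia, thrombocytopenia with significant bleeding, and febrile neutropenia. For short or non-bleeding Grade 4 events the answer depends on the unspecified row. Taken literally that row captures them, since its exclusions name no cytopenia. Taken as covering only what the rows above leave out, it does not. Grade 3 fatigue is outside the gate on either reading.
- **That the first six at 10 mg escape the 30% rule.** Seven is when the rule starts, not whom it counts.
- **That the duration condition on neutropenia cannot be checked because Section 4.1 gives the run-in women a** "One-time safety assessment for first six patients who re-register to ANA10". Footnote 4 there moves the end-of-Cycle-2 blood count to the time of discontinuation, and Section 8.2 discontinues the drug for a related Grade 4 event. A further count is due 30 days after the last dose.

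**Conclusion.** The point holds as a mismatch between two safety rules for the same women. It follows from the rules themselves that three of six gap events, or two plus one DLT that Section 16.42 also counts, reopen re-registration and then meet the halt limit when a seventh woman starts. It also follows that two of six would halt the approved-dose cycles but not the 10 mg cycle.

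The practical size is small. With no DLTs, reopening into a halt has probability 0.2% at g = 5% and 1.6% at g = 10%. These rates are assumptions. The higher rows of the table have no support in the documents: Section 1.4 describes toxicity at 10 mg as comparable with 1 mg, and the fatigue entry in Section 10.32 is a reporting exemption, not an incidence. A halt is temporary, and the primary estimate and its power are unaffected. The change is worth making because it is cheap and concerns a safety gate, not because the present rule is likely to cause harm.

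**What to change.** In Section 16.42(b), start the 30% count at six women instead of seven. In Sections 1.41 and 7.41, require that count to be checked, on the events known at the time, before re-registration reopens, and hold for review if it is 30% or more. Two of six then triggers a review at 10 mg, as it does at 1 mg and letrozole.

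At minimum, hold when three or more of six have a counted event, because that result already meets the halt limit at seven.

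Leave the DLT table unchanged. Because Section 16.42 counts every Grade 4 cytopenia, the check works whichever way the unspecified row is read.

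The cost is one number and one added clause in each of two sections, plus agreement with the FDA, since the run-in was set up at its request. No visits, tests or patients are added. With no DLTs, the two-of-six limit adds a temporary review with probability 3.3% at g = 5% and 11.4% at g = 10%; the three-of-six minimum adds one with probability 0.2% and 1.6%. The two-of-six limit does bring events that the DLT table sets aside, such as Grade 3 fatigue and unrelated events, into the decision to reopen. The sponsor should accept that openly or choose the three-of-six version.
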